#### **4.3 Study Stopping Criteria**

If any of the following occur, the study will be temporarily paused until a full review by the safety monitoring committee is completed:

- Any death (other than death related to progressive disease) that occurs within 30 days of study drug administration.

#### **4.4 End of Study**

The end of the study is defined as the date of the last visit of the last patient undergoing the trial.

#### **4.5 Duration of Therapy**

Maintenance therapy will continue for a maximum of 12 cycles (28 days/cycle) from first dose of APR-246, or until one of the following criteria applies:

- Evidence of disease relapse defined as  $\geq 5\%$  blasts for AML patients or  $>5\%$  blasts for MDS patients. Patients who are continuing to derive clinical benefit in the opinion of the investigator may remain on study treatment following relapse.
- Inter-current illness that prevents further administration of treatment.
- Unacceptable AEs.
- Participant decides to withdraw from treatment.
- General or specific changes in the patient's condition render the patient unacceptable for further treatment in the judgment of the investigator.
- Participant begins other treatment for underlying disease (MDS or AML).
- Grade 3-4 acute GVHD or Severe chronic GVHD.

If the participant discontinues treatment early, then the reason for treatment discontinuation and the date the participant was removed will be documented. Participants removed from treatment for unacceptable AEs will be followed until resolution or stabilization of the AE. Participants that discontinue treatment early will continue to be followed for relapse, if not yet documented, and survival.

Patients may continue to receive study treatment in the setting of relapse or progression, up to a maximum of 12 cycles, provided they are continuing to derive benefit in the opinion of the Investigator.

#### **4.6 Trial Discontinuation**

For reasonable cause, either the Investigator or the Sponsor may terminate this study prematurely. Written notification of the termination is required. Conditions that may warrant termination include, but are not limited to:

- The discovery of an unexpected, significant, or unacceptable risk to the patients enrolled in the study.
- Failure of the Investigator to enter patients at an acceptable rate.
- Insufficient adherence to protocol requirements (non-compliance).
- Lack of evaluable and/or complete data.
- Decision to modify the developmental plan of the drug.
- A decision on the part of the Sponsor to suspend or discontinue development of the drug.

#### **4.7 Drug Accountability/Disposition of Clinical Trial Supplies**

Drug accountability records will be maintained for all clinical trial supplies.

All unused clinical trial supplies will be returned to the Sponsor, or at the Sponsor's directive, destroyed by the site following site standard practices for disposal.

#### **4.8 Registration**

Prior to registration and any study-specific evaluations being performed, all patients must have given written informed consent for the study and must have completed the pre-study evaluations. Patients must meet all eligibility requirements listed in Section 5.0. Patients will be registered on the study by using the [REDACTED] Interactive Web Response System (IWRS) automated patient registration system (see the Study Operations Manual for specific instructions).

## 5.0 SELECTION AND WITHDRAWAL OF SUBJECTS

To participate in this study, patients must meet:

- Transplant and enrollment criteria in Sections 5.1.1-5.1.2; and,
- APR-246 and azacitidine treatment criteria in Sections 5.2.1-5.2.2.

### 5.1 Pre-Screening

#### 5.1.1 Inclusion Criteria

These observations will be done  $\leq$  28 days prior to beginning conditioning chemotherapy in anticipation for allograft infusion.

1. Documentation of a *TP53* gene mutation (which is not benign or likely benign) by NGS based on local evaluation with study eligibility confirmed centrally.
2. Must provide a pre-HSCT bone marrow biopsy.
3. Age  $\geq$ 18 years at the time of signing the informed consent form
4. Institutional Review Board/Independent Ethics Committee (IRB/IEC) approved written informed consent and privacy language as per national regulations (e.g., Health Insurance Portability and Accountability Act Authorization (HIPAA) for US sites) obtained from the participant or legally authorized representative prior to any study-related procedures (including withdrawal of prohibited medication, if applicable).
5. Patient has confirmed, morphologically documented MDS or AML by WHO criteria.
6. Patient is considered a suitable candidate for HSCT and has an acceptable source of allogeneic donor hematopoietic stem cells, as defined per institutional practice (allogeneic HSCT for any donor source [matched sibling, unrelated donor (URD), mismatched URD, related haploidentical] and any graft source [BM, PB], and any non-study conditioning [myeloablative conditioning (MAC), reduced intensity conditioning (RIC), or non-myeloablative conditioning (NMA)] will be permitted). Additionally, any standard (non-study) GVHD prophylaxis regimen will be permitted.
7. Females must either:
  - a. Be of non-childbearing potential
    - i. postmenopausal (defined as at least 1 year without menses) prior to screening, or
    - ii. documented as surgically sterilized at least 1 month prior to the screening visit

- b. Or, if of childbearing potential,
  - i. Agree not to try to become pregnant during the study and for 6 months after the final study drug administration
  - ii. And have a negative serum pregnancy test at screening
  - iii. And, if heterosexually active, agree to consistently use highly effective contraception per locally accepted standards in addition to a barrier method starting at screening and throughout the study period and for 6 months after final study drug administration.
8. Females must agree not to breastfeed or donate ova throughout the study drug treatment period and for 6 months after the final study drug administration.
9. Males (even if surgically sterilized), and their partners who are women of childbearing potential must be using highly effective contraception in addition to a barrier method throughout the study drug treatment period and for 127 days after the final study drug administration.
10. Males must not donate sperm throughout the study drug treatment period and for 127 days after the final study drug administration.

### **5.1.2 Exclusion Criteria**

1. Patient has had a prior allogeneic transplant.
2. Patient has any of the following cardiac abnormalities (as determined by treating physician):
  - a. Myocardial infarct within six months prior to registration
  - b. New York Heart Association Class III or IV heart failure or known left ventricular ejection fraction (LVEF) < 40%
  - c. A history of familial long QT syndrome
  - d. Symptomatic atrial or ventricular arrhythmias not controlled by medications
  - e. QTc  $\geq$  470 ms calculated from a mean of 3 ECG readings using Fridericia's correction ( $QTcF = QT/RR^{0.33}$ ). Patients with QTc  $\geq$  470 ms and bundle branch block and/or pacemaker rhythm may be enrolled after approval by Medical Monitor.

## **5.2 Post-transplant Criteria for APR-246 and Azacitidine Treatment**

### **5.2.1 Inclusion Criteria**

1. Patient has received one allogeneic transplant for AML or MDS. At time of

treatment, patient must be in morphologic remission for AML or MDS as defined as < 5% blasts for AML and ≤ 5% blasts for MDS, and in cytogenetic remission with no morphologic characteristics of acute leukemia (e.g., Auer Rods) in the BM with no evidence of extramedullary disease such as central nervous system involvement or granulocytic sarcoma. Patients with CR with incomplete count recovery (CRp or CRI) are allowed. Incomplete platelet recovery (CRp) is defined as CR with platelet count < 100 x 10^9/L. Incomplete blood count recovery (CRI) is defined as CR with neutropenia < 1 x 10^9/L with or without complete platelet recovery. Red blood cell count (RBC) and platelet transfusion independence is not required.

2. Any standard (non-study) conditioning [MAC, RIC, or NMA] will be permitted. Acceptable source of allogeneic donor hematopoietic stem cells, as defined per institutional practice (allogeneic HCT for any donor source [matched sibling, URD, mismatched URD, related haploidentical] and any graft source [BM, PB].
3. Patient is ≥ 30 days and ≤ 100 days from hematopoietic cell infusion.
4. Patient is in complete remission after the transplant and has achieved engraftment. Engraftment is defined as ANC≥500/µL and platelets ≥ 20000/µL on 3 consecutive measurements (each occurring at least 1 day apart). The patient must not have had a platelet transfusion within 7 days prior to the first measurement.
5. Patients who have developed grades II-IV acute GVHD will be allowed to initiate maintenance therapy based on the following criteria:
  - Does not require high dose steroids as defined as dosage of > 0.5 mg/kg of prednisone (or equivalent) daily dose within 1 week of post-HSCT screening
  - No escalation of systemic immunosuppression in terms of increase of corticosteroids or addition of new agent/modality within 2 weeks of post-HSCT screening. Dose adjustments (both increase and decrease) of GVHD preventative medications such as calcineurin inhibitors or sirolimus to achieve therapeutic trough levels, is allowed. Topical skin and topical gastrointestinal steroids are allowed.
6. Females must either:
  - Be of non-childbearing potential
    - postmenopausal (defined as at least 1 year without menses) prior to screening, or
    - documented as surgically sterilized (e.g., hysterectomy or tubal ligation) at least 1 month prior to the screening visit
  - Or, if of childbearing potential,
    - Agree not to try to become pregnant during the study and for 6 months after the final study drug administration

- And have a negative serum pregnancy test at screening
- And, if heterosexually active, agree to consistently use highly effective contraception per locally accepted standards in addition to a barrier method starting at screening and throughout the study period and for 6 months after final study drug administration.

7. Females must agree not to breastfeed or donate ova throughout the study drug treatment period and for 6 months after the final study drug administration.
8. Males (even if surgically sterilized), and their partners who are women of childbearing potential must be using highly effective contraception in addition to a barrier method throughout the study drug treatment period.
9. Males must not donate sperm throughout the study drug treatment period.
10. Agrees not to participate in another interventional study while on treatment.
11. Karnofsky Performance Status 70 or greater is required. (APPENDIX A)
12. Patient has adequate organ function as defined by the following laboratory values:
  - a. Creatinine clearance > 30 mL/min by Cockcroft-Gault formula;
  - b. Total serum bilirubin < 1.5 x ULN unless due to Gilbert's Syndrome, underlying disease of MDS, hemolysis or considered an effect of regular blood transfusions;
  - c. ALT/AST < 2.5 x ULN, unless due to underlying disease of MDS.

### **5.2.2 Exclusion Criteria**

1. Use of umbilical cord blood donor and stem cell source.
2. Patient has uncontrolled infection. Definitive therapy for infection is required and must have no signs of progression within 7 days of first day of study drug treatment.
3. Use of investigational agent within 14 days of pre-HSCT screening or anytime thereafter.
4. Use of hypomethylating agent, cytotoxic chemotherapeutic agents, or experimental agents (agents that are not commercially available) for the treatment of MDS or AML within 14 days of the first day of pre-HSCT screening or anytime thereafter.
5. Patient has used experimental therapy for acute GVHD at any time post-transplant. If unsure of the definition of "experimental", discussion with the Medical Monitor is recommended.
6. Patient requires treatment with supplemental oxygen not including usage of non-invasive CPAP at night.
7. Patient has any of the following cardiac abnormalities (as determined by

treating physician):

- a. Myocardial infarct within six months prior to registration
- b. New York Heart Association Class III or IV heart failure or known LVEF< 40%
- c. A history of familial long QT syndrome
- d. Symptomatic atrial or ventricular arrhythmias not controlled by medications
- e. QTc  $\geq$  470 ms calculated from a mean of 3 ECG readings using Fridericia's correction ( $QTcF = QT/RR^{0.33}$ ). Patients with QTc  $\geq$  470 ms and bundle branch block and/or pacemaker rhythm may be enrolled after approval by Medical Monitor.

### **5.3 Withdrawal Criteria**

Protocol therapy will be discontinued at any time if any of the following situations occur:

1. Relapsed disease, unless Investigator believes patient is receiving clinical benefit.
2. The development of toxicity which, in the Investigator's judgment, precludes further therapy.
3. Patient refusal.
4. Lost to follow-up/noncompliance.
5. Intercurrent illness.
6. At the discretion of the Investigator.
7. Pregnancy.
8. Study termination.
9. Initiation of anti-MDS/AML therapy or DLI for purpose of treating MDS/AML.

#### **5.3.1 Withdrawn Subjects**

When a patient is removed from the study, the Investigator will clearly document the reason in the medical record and complete the appropriate case report form page describing the reason for discontinuation. In addition, every effort should be made to complete the appropriate assessments listed in Section 7.3.

### **5.4 Noncompliance**

All instances of noncompliance and all resulting protocol deviations will be entered in the case report forms.

## 6.0 TREATMENT OF SUBJECTS

### 6.1 Drug Preparation and Administration

Patients will receive APR-246 and azacitidine on days 1-4 and 1-5, respectively, every 28-day cycle. APR-246 and azacitidine are administered in the clinic.

**Figure 2: Overview of APR-246 and Azacitidine Treatment Per Cycle**

APR-246 administration	↓	↓	↓	↓			Next Cycle:
Day	1	2	3	4	5	6-28	D29 prior cycle/D1
Azacitidine administration	↑	↑	↑	↑	↑		+4 wk window permitted

#### 6.1.1 APR-246

At the pharmacies, the IMP vials are to be stored at 2-8°C (35.6-46.4°F). At the pharmacies and at the study centers, the prepared APR-246 study product (diluted in sodium chloride solution) is to be stored at not more than 25°C. The infusion should be completed within 24 hours from the time of preparation (see Study Manual).

A fixed dose of 3.7g APR-246 will be administered as an intravenous infusion daily on days 1-4 of each 28 day cycle. Total infusion time is 4 hours, administered in 2 consecutive steps:

- 1) 1.6 g for the first 45 minutes (+/- 2 min)
- 2) 2.1 g over 3 hours 15 minutes (+/- 15 min)

Detailed instructions on vial concentration, preparation and dispensing can be found in the Pharmacy Manual. The infusion timing, including start/stop times and the time of rate change, must be recorded.

#### 6.1.2 Azacitidine

Azacitidine (36 mg/m^2) is administered sc or iv for 5 consecutive days. The same route of administration should be used each day of a cycle.

Azacitidine will be administered within 1 hour following the end of the APR-246 infusion.

## 6.2 Criteria for Retreatment and Dose Modifications

This section outlines the requirements for proceeding with treatment with APR-246, and the protocol rules for APR-246 dose modification due to toxicity.

### ECGs

#### For all patients

- Patients with screening QTcF  $\geq 470$  ms (average from triplicate ECG) are excluded from the study. Rescreening is allowed.
- At a minimum, ECG should be performed pre-dose and end-of-infusion (EOI) on Day 1, Cycle 1-4. This ECG may be done as single or replicate (i.e. duplicate or triplicate, average QTcF should be used). Patients with screening or any pre-dose  $450 \leq QTc < 470$  ms should be subject to more intense ECG monitoring (see below).
- If a pre-dose ECG shows QTcF  $\geq 470$  ms the QTc reading should be manually confirmed. Serum concentrations of electrolytes should be controlled and adjusted if necessary. Concomitant medication should be reviewed and adjusted if necessary. A new ECG may be done at any time, even the same day. The patient should not be treated unless QTc is  $< 470$ . If the dose is given later on the same day, follow the planned cycle. If the dose cannot be given, omit that dose from the cycle.
- If the patient at any time during the study starts with a concomitant medication known to prolong the QT interval, a pre-dose and EOI ECG should be performed for the next planned dose
- If any ECG during the study shows a significant change (vs baseline or pre-dose) in QTcF, defined as either i) increase  $> 60$  ms, ii) increase  $> 25\%$ , or iii) increase to an absolute value  $\geq 500$  ms, the dose should be held/interrupted. If the QTc prolongation is confirmed by a manual read, the therapy should stop until the cause has been identified and eliminated (electrolyte disturbance or concomitant drug) and QTc is again  $< 470$  ms. Discontinue APR-246 permanently, if other causes for clinically significant QTcF increase are excluded.

#### Additional monitoring for patients with $450 \leq QTc < 470$ ms at baseline or any pre-dose measurement

- ECG should be performed pre-dose and end-of-infusion (EOI) for all doses (Day 1-4, all cycles). This ECG may be done as single or replicate (i.e., duplicate or triplicate, average QTcF should be used).
- Dose should be held for pre-dose QTcF  $\geq 470$  ms (see above). For a post-dose

(EOI) ECG showing >60 ms increase vs pre-dose or any QTcF >500 ms, see above.

- Patients should avoid QTc prolonging drugs on infusion days, if possible, and have any electrolyte imbalance checked and corrected (CTCAE ≤Grade 1).
- If repeated QTcF measurements show a stable QTcF <450, or if the patient is stable in the interval 450 to <470 ms with no significant change at EOI (several cycles of treatment) the investigator may discuss with the Medical Monitor to decrease the number of ECGs performed in the study.

### **Other toxicity**

All dose modifications, interruptions or discontinuations must be based on the worst preceding toxicity as graded by the NCI Clinical Toxicity Criteria (NCI-CTCAE version 5). Once a dose has been reduced during a treatment cycle, re-escalation will not be permitted during any subsequent cycle (with exception of CNS events). If the administration of APR-246 is interrupted for reasons other than toxicity, then treatment with APR-246 may be resumed at the same dose. The same provision applies if the patient experienced an unacceptable toxicity not specifically described in this section, provided that this toxicity resolved to ≤ CTCAE grade 1, unless otherwise specified.

Day 1 of next cycle treatment with APR-246 and azacitidine can be delayed for up to 4 weeks (28 days) to allow for count recovery at Investigator discretion pending discussion with the Sponsor and Medical Monitor. Non-hematologic grade 4 treatment related adverse events will lead to permanent discontinuation, irrespective of recovery time, unless otherwise specified.

Exceptions would include nausea/vomiting/diarrhea which can be controlled by medications and/or asymptomatic electrolyte imbalances which can be corrected. In addition, in most instances, patients that experience a prolonged treatment interruption because of an adverse event and/or a grade 3 adverse event will decrease the dose of study drug after their recovery (see tables in this section for dose adjustment guidelines).

If any other drug-related grade 3 or 4 toxicity that is not clearly related to azacitidine is observed, APR-246 dose must be reduced for the next and subsequent cycles.

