Grade 3	If resolved with medical therapy, continue same dose level If not resolved despite treatment interruption and maximal medical therapy, stop infusion and ↓ 1 dose level for subsequent dose
Grade 4	Permanently discontinue patient from APR-246.
Infusion Related Reaction	
Grade 1	Maintain dose level.
Grade 2	Maintain dose level; Symptomatic management (e.g., antihistamines, corticosteroids, narcotics, IV fluids)
Grade 3	If resolved in < 4 hours with treatment interruption and medical therapy (e.g., antihistamines, corticosteroids, narcotics, IV fluids), continue same dose level and rate. If not resolved in < 4 hours despite treatment interruption and maximal medical therapy, stop infusion and ↓ 1 dose level for subsequent dose
Grade 4	Permanently discontinue patient from APR-246.
Nausea/Vomiting/Diarrhea	
Grade 1	Maintain dose level
Grade 2	If resolved, then maintain dose level If not resolved despite maximal medical therapy, then ↓ 1 dose level
Grade 3	If resolved, then maintain dose level If not resolved despite maximal medical therapy, then ↓ 1 dose level
Grade 4	Permanently discontinue patient from APR-246
Any Other Toxicity	
Grade 3 or 4	Delay dose until resolution to ≤ Grade 1, then ↓ 1 dose level

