**Table 6. Recommendations for prevention and treatment of cancer-related infections**

Organism	Recommendations
Bacterial	Consider fluoroquinolone or other suitable anti-bacterial prophylaxis during neutropenia

Fungal	Consider prophylaxis during neutropenia and for anticipated mucositis. Assess risk for Pneumocystis jirovecii pneumonia and select agent(s) as clinically indicated.
Viral	Start treatment with anti-viral medication in the setting of neutropenia and continually assess the risk for viral infection during treatment with anti-cancer therapy.

Refer to Section 6.2 for guidance on APR-246 dose modification in the setting severe infection and/or infestation event, using the parameter titled, "Any Other Toxicity" (Table 5).

Refer to Section 6.3 for a description of drugs that are not allowed to be used while a patient is on study treatment.

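### Section 6.2 and Table 5 conflict on grade 4 nausea/vomiting/diarrhea that medication controls, and on grade 4 non-hematologic events with no table row of their own

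*Combined protocol and SAP*

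**What the plan says.** Section 6.2, under Other toxicity, gives the general rule: "Non-hematologic grade 4 treatment related adverse events will lead to permanent discontinuation, irrespective of recovery time, unless otherwise specified". The following paragraph starts with what is left out of it: "Exceptions would include nausea/vomiting/diarrhea which can be controlled by medications and/or asymptomatic electrolyte imbalances which can be corrected". The subsection closes with a different instruction, which applies to the next cycle and those after it: "If any other drug-related grade 3 or 4 toxicity that is not clearly related to azacitidine is observed, APR-246 dose must be reduced". Near its start, the same subsection allows APR-246 to resume at an unchanged dose after some interruptions, and adds: "The same provision applies if the patient experienced an unacceptable toxicity not specifically described in this section". That sentence requires recovery to grade 1 or below and also yields to any other specification.

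Table 5 (Section 6.2.1) gives one instruction for grade 4 nausea/vomiting/diarrhea: "Permanently discontinue patient from APR-246". Its final row, for all remaining toxicity of grade 3 or 4, reads: "Delay dose until resolution to ≤ Grade 1, then ↓ 1 dose level".

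Below Table 6, the infection guidance says: "Refer to Section 6.2 for guidance on APR-246 dose modification in the setting severe infection and/or infestation event". It then names the catch-all row of Table 5 as the one to use.

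Section 4.2 lowers the APR-246 dose for later patients if more than 1 of the first 6 has a listed toxicity. The first item on the list is treatment-related non-hematological toxicity of grade 3-4 that results in either a dose change or withdrawal.

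**The concern.** A site that meets a grade 4 event should find one instruction. For two kinds of event it finds at least two, and they differ on whether the patient receives APR-246 again. In a multi-center trial, patients with the same event could then be stopped at one site and re-treated at another.

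Safety and tolerability is a primary objective (Section 3.1). Rates of discontinuation and the amount of drug received are part of how tolerability is judged, so they should reflect the treatment and not which paragraph a site happened to follow. Patient safety is also involved, since the passages disagree about re-exposure after a grade 4 event.

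**Working it through.** No arithmetic applies. The check sets the grade 4 instruction in the Section 6.2 text beside that in Tables 3 and 5, toxicity by toxicity.

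| Grade 4 event | Section 6.2 text | Table | Result |
|---|---|---|---|
| Creatinine, bilirubin | Stop | Table 3: stop | Agree |
| AST/ALT (row limited to cases without bilirubin above 2.0 × ULN) | Stop | Table 3: stop | Agree |
| CNS events | Stop | Table 5: stop | Agree |
| Infusion related reaction | Stop | Table 5: stop | Agree |
| Nausea/vomiting/diarrhea, controllable by medication | Exempt from stopping | Table 5: stop, no exception | Direct conflict |
| Treatment-related non-hematologic event without its own row | Stop by the general rule; reduce by the last sentence | Table 5 catch-all: delay, then reduce one level | Conflict unless the proviso settles it |

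Of the four categories in Table 5, two agree with the text and two do not.

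**Nausea/vomiting/diarrhea.** The proviso in the general rule cannot settle this, because text and table both specify and they differ. Nor can the table be read as meaning only uncontrolled cases. Its grade 2 and grade 3 rows separate events that resolve from those that do not; its grade 4 row makes no such split.

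**Events without a row.** Suppose the catch-all row counts as a different specification and so displaces the general rule. The named grade 4 rows in Tables 3 and 5 already stop treatment, and the catch-all takes nearly everything else. The general rule is then left with almost no effect. The named exception for correctable electrolyte imbalances also loses its purpose, since the catch-all would already have spared those patients from permanent stopping. Suppose instead that the general rule governs. Then both the catch-all at grade 4 and the last sentence of the subsection are contradicted. The text uses mandatory wording, while the title of Table 5 calls its contents recommended. No order of precedence is given. The sentence on resuming at the same dose adds a third possible reading, but a weaker one: it yields to other specifications, and two of those ask for a reduction.

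**First-6 rule (Section 4.2).**
- A treatment-related event without its own row counts if it leads to stopping and also counts if it leads to dose reduction, so choosing between those two instructions does not change the tally.
- A controlled, treatment-related grade 4 nausea/vomiting/diarrhea event is a withdrawal under Table 5 and counts. Under the text's exception the patient may continue. If this happens without a dose change, the first criterion is not met. The separate criterion for nausea/vomiting/diarrhea names only grade 3 that persists beyond 28 days. More than 1 of 6 means at least 2, so one such event could decide whether the dose is lowered for later patients.

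**The case against.** The strongest reply is that the general rule defers to other specifications, a nearby sentence refers to the tables for dose adjustment, and the last sentence of the subsection agrees with the catch-all on reducing and continuing. On this view the text and Table 5 form one system, and the general rule is merely redundant. This reply has weight: the disagreement over unlisted events lies partly within Section 6.2 itself and is not simply text against table. It does not dispose of the point. The reference to the tables sits in the sentence on prolonged interruptions and grade 3 events, and a stopping rule that applies to almost nothing is unlikely to be what was meant. The reply does not touch the nausea/vomiting/diarrhea conflict.

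A reader might also infer more than the documents support:

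- *That text and tables conflict for grade 4 non-hematologic toxicity in general.* They agree on every other listed category in the table above.
- *That severe infection is left under two rules.* The guidance below Table 6 names the row to use, which is a fair instance of a different specification. An infection judged unrelated to treatment is outside the general rule in any case.
- *That the first-6 tally is open for every such event.* Only the controlled nausea/vomiting/diarrhea case can differ between stopping under the table and continuing under the text.
- *That the number of patients can be stated.* An assumed 5-20% of 31 would be 0.05 × 31 = 1.6 to 0.20 × 31 = 6.2 patients. The rate has no basis in the documents, and it would include events on which text and tables agree.

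**Conclusion.** The point holds for two kinds of event. One is a direct contradiction: grade 4 nausea/vomiting/diarrhea that medication can control. The other is an unresolved precedence: treatment-related grade 4 non-hematologic events without a row of their own.

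Exposure and discontinuation rates can differ between sites. So can summaries by dose level (Sections 8.5.5 and 9.1), if these follow the dose actually received. The first-6 decision is exposed only to the controlled nausea/vomiting/diarrhea case, and only if the patient continues without a dose change.

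The sample size in Section 9.2 and the RFS definition in Section 9.3.1 are unaffected. Patients who stop early remain in follow-up for relapse and survival (Section 4.5), and the RFS censoring rule mentions stopping for toxicity only together with withdrawal of consent. The primary safety endpoint concerns the incidence, severity and relatedness of adverse events (Section 3.4.1), so its definition does not depend on which instruction is followed. The size of the effect in patients cannot be derived from the documents. Which clinical rule is right is not judged here.

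**What to change.** The sponsor's clinical team should reconcile the Other toxicity text of Section 6.2, including its exceptions and its last sentence, with the nausea/vomiting/diarrhea and catch-all rows of Table 5. After the change, each grade 4 event should lead to one instruction, and the protocol should say whether text or table prevails where they differ. The sentence on resuming at the same dose should be checked in the same pass. Once the nausea/vomiting/diarrhea instruction is settled, Section 4.2 should make clear whether a controlled grade 4 event of that kind counts among the first 6 patients. No clinical rule is proposed.

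The cost is protocol wording in an amendment. No patients or analyses are added. Dose changes and reasons for stopping are already recorded (Sections 4.5, 5.3.1 and 6.2.1), so no new data collection is needed.
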